## **10.0 Protection of Human Subjects**

The study should receive approval from the Institutional Review Board (IRB) of the each institution, and then a written study agreement should be made with institutions before the initiation of the study in each institution.

Patient written authorization form to use and/or disclose personal and/or health data from subjects must be obtained prior to enrolling the subject and the investigator is required to document this authorization.

Subject confidentiality must be maintained at all times; therefore demographics that could identify the patients will not be collected.

Monitoring for any sites is not required. However internal consistency check for completeness and consistency of data will be done to ensure integrity of the information reported.

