### **11.1.5 Serious Adverse Event Reporting**

This protocol requires all SAEs as outlined in protocol section 11.1.1 to be actively solicited. The safety profile of adalimumab which has over 3.5 million PYs of post-marketing exposure is stable and well established; non-serious events will not be actively solicited as these events are not likely to contribute to the further understanding of the safety profile of the product. Any non-serious AEs will be collected as spontaneous reports if AbbVie is notified.

In the event of a serious adverse event, and additionally, any non-serious event of malignancy in patients 30 years of age and younger, whether related to study drug or not,

the physician will notify the AbbVie contact person identified below within 24 hours of the physician becoming aware of the event.

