6.4 Safety Endpoint Analysis Method

6.4.1 Adverse Events (AEs)

The AE status for each of the following items is presented in a summary table. In the summary table, the number of subjects with AE, incidence rate (%), 95% confidence interval for the incidence rate, and number of events will be included.

- AEs that caused discontinuation of the study drug
- Adverse drug reactions (ADRs)^a that caused discontinuation of the study drug
- Serious adverse events (SAEs) that caused discontinuation of the study drug
- Serious adverse drug reactions (SADRs)^a that caused discontinuation of the study drug
- SAEs that occurred during the entire study period

| dreamcis ATIGERMED COMPANY | | Last Update Date |
|----------------------------------|--|---------------------------------------|
| | CONFIDENTIAL: | · · · · · · · · · · · · · · · · · · · |
| | THIS DOCUMENT AND THE INFORMATION CONTAINED HEREIN ARE | 02-NOV-2018 |
| A LIGERMED COMPANY | PROPRIETARY TO THE COMPANY AND ARE NOT TO BE DISCLOSED WITHOUT THE WRITTEN PERMISSION OF THE COMPANY | 02-1NO V-2018 |
| | WITHOUT THE WRITTEN PERMISSION OF THE COMPANY. | |
| STATISTICAL ANALYSIS PLAN (V2.0) | | |

For the following items, the AE status will be presented in detail. Using MedDRA, the number of subjects, incidence rate (%), 95% confidence interval for the incidence rate, and number of events will be included by SOC and PT. Here, even if two or more events occurred in one subject, if they fall under one category, they will be analyzed as one subject in the category. Also, one subject may be presented as a duplicate in different AE categories.

- AEs that caused discontinuation of the study drug
- ADRs^a that caused discontinuation of the study drug
- SAEs that caused discontinuation of the study drug
- SADRs^a that caused discontinuation of the study drug
- SAEs that occurred during the entire study period

For the AEs that caused discontinuation of the study drug, the number of events for the AE items below will be presented.

- Severity
- Outcome
- Causality

As for "severity" and "causality" among the AE items, the AE status will be presented in detail. Using MedDRA, the number of subjects, incidence rate (%), and number of events will be included by SOC and PT. Here, even if two or more events occurred in one subject, if they fall under one category, they will be analyzed as one subject in the category. Also, one subject may be presented as a duplicate in different AE categories.

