6.5 Exploratory Analysis

(1) Logistic regression

The exploratory analysis will focus on identifying the potential predictors for the clinical effectiveness of adalimumab (persistent clinical response at weeks 8 and 56, clinical response at weeks 8 and 56, clinical remission, clinical response without steroid administration, clinical remission without steroid administration, mucosal healing, and below 250 fecal calprotectin level).

To confirm the predictors, univariate logistic regression will be performed for each factor, and then multiple logistic regressions will be performed for the significant predictors.

Here, the independent variables shown below will be considered predictors, but the variables to be used in the actual analysis can be added or subtracted considering the collected data and characteristics.

- Gender
- Onset age
- **BMI**
- Disease duration
- Full Mayo score
- Fecal calprotectin level
- UC extent
- CRP
- Albumin
- Trough level of adalimumab
- Concomitant medication for UC
- TNF antagonist naivety
- Dose escalation
- (2) Percentage of subjects according to the fecal calprotectin level at baseline, visit 2 (week 8), and visit 8 (week 56)

The frequency and percentage of subjects with a below 250 fecal calprotectin level at baseline, visit 2

^a Adverse drug reaction (ADR): Adverse events with "probable," "possible," "probably not," or "not assessable" causality

^b PTYs = Sum of the total administration period (days) of all the subjects / 365.25

[°] AE incidence rate per 100 PTY = {(Number of AEs)/(PTYs)}×100

| dreamcis A TIGERMED COMPANY | | Last Update Date |
|----------------------------------|---|------------------|
| | CONFIDENTIAL: | |
| | THIS DOCUMENT AND THE INFORMATION CONTAINED HEREIN ARE PROPRIETARY TO THE COMPANY AND ARE NOT TO BE DISCLOSED | 02-NOV-2018 |
| | WITHOUT THE WRITTEN PERMISSION OF THE COMPANY. | |
| STATISTICAL ANALYSIS PLAN (V2.0) | | |

STATISTICAL ANALYSIS PLAN (V2.0

(week 8), and visit 8 (week 56) will be presented.

(3) Percentage of subjects according to the CRP level at baseline, visit 2 (week 8), and visit 8 (week 56)

The frequency and percentage of subjects with a CRP level of below 5 mg/L at baseline, visit 2 (week 8), and visit 8 (week 56) will be presented.

(4) Clinical response at each visit depending on the TNF antagonist naivety

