6.6 Missing Data Handling and Analysis Method

If there are any missing or incomplete data, they shall be handled as shown below.

- If there is any missing value in the demographic data, it shall not be replaced and shall be analyzed as it is.
- For the Mayo score for the evaluation of the clinical response, clinical remission, and mucosal healing among the effectiveness endpoints, if a missing value occurs at a certain point, it shall be handled as shown below.
 - If a missing value occurs at the partial Mayo score (stool frequency, rectal bleeding, physician's
 global assessment), the most recently obtained value shall be analyzed as if it were obtained at the
 time (LOCF method).
 - If a missing value occurs at the endoscopic findings subscore in the full Mayo score, it shall not be replaced and shall be analyzed as it is.
- Among the continuous data used in the analysis, the data that include a sign of inequality, symbols, etc. (e.g., "over 20," ">20") shall be excluded from the analysis.

| | | Last Update Date |
|----------------------------------|---|------------------|
| dreamcis ATIGERMED COMPANY | CONFIDENTIAL: THIS DOCUMENT AND THE INFORMATION CONTAINED HEREIN ARE PROPRIETARY TO THE COMPANY AND ARE NOT TO BE DISCLOSED WITHOUT THE WRITTEN PERMISSION OF THE COMPANY. | 02-NOV-2018 |
| STATISTICAL ANALYSIS PLAN (V2.0) | | |

- If only some information of the date used in the continuous data analysis is present and it is therefore not computable, it shall be excluded from the analysis.
- If there is any missing value in the safety data, it shall not be replaced and shall be analyzed as it is.

| dreamcis ATIGERMED COMPANY | | Last Update Date |
|----------------------------------|---|------------------|
| | CONFIDENTIAL: THIS DOCUMENT AND THE INFORMATION CONTAINED HEREIN ARE | |
| | PROPRIETARY TO THE COMPANY AND ARE NOT TO BE DISCLOSED WITHOUT THE WRITTEN PERMISSION OF THE COMPANY. | 02-NOV-2018 |
| STATISTICAL ANALYSIS PLAN (V2.0) | | |

References

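### A discontinuation AE whose causality stays blank after queries adds nothing to the SAP's ADR and serious-ADR rows, although the definition counts even events rated not assessable

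*SAP*

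**What the plan says.** Two SAP rules meet here.

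- **ADR definition.** Footnote a to SAP 6.4.1, which prints within section 6.5, reads: "Adverse events with 'probable,' 'possible,' 'probably not,' or 'not assessable' causality". A missing causality is not among the four labels. The SAP's revision table records that the probably-not category was added in V2.0.
- **Missing safety data.** SAP 6.6 states: "If there is any missing value in the safety data, it shall not be replaced and shall be analyzed as it is". It makes no exception for causality.

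The rows that depend on footnote a are "Adverse drug reactions (ADRs)^a that caused discontinuation of the study drug" and "Serious adverse drug reactions (SADRs)^a that caused discontinuation of the study drug". Both appear in the summary table, in the table by system organ class and preferred term, and in the subject listings. The two tables also give 95% confidence intervals.

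Other outputs in SAP 6.4.1 do not use the ADR definition: AEs and serious AEs that caused discontinuation, their rates per 100 patient-years, and "SAEs that occurred during the entire study period". For AEs that caused discontinuation, the SAP also asks for event counts by causality and a breakdown of causality by organ class and term.

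SAP 2.5.3 places the safety analysis on the ITT set.

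**The concern.** Footnote a is inclusive. An event the physician could not assess counts as an ADR, and so does one judged probably not related. A form marked not assessable therefore enters the ADR rows, while the same form left blank does not. The missing-data rule works against the direction the definition takes.

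The effect has one sign. A blank can remove an event from the ADR and serious-ADR rows but can never add one. These are the rows a reader would use for drug-related discontinuation, and their confidence intervals would shift with the lowered rate.

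Some features of the study make blanks possible. Protocol 11.1.5 says: "Any non-serious AEs will be collected as spontaneous reports". Protocol 10.0 says: "Monitoring for any sites is not required". Under Protocol 9.2.2, stopping adalimumab is itself a reason for drop-out, after which collection is limited to the drop-out reason and serious AEs.

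**Working it through.** **Step 1: follow one event through the rules.** Take an AE that caused discontinuation and whose causality is still blank when the database is final.

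| Output in SAP 6.4.1 | Needs a footnote-a label? | Blank-causality event counted? |
|---|---|---|
| AEs that caused discontinuation (tables, listing, rate per 100 patient-years) | No | Yes |
| Serious AEs that caused discontinuation (same outputs) | No | Yes, if serious |
| Serious AEs over the whole study (tables, listing) | No | Yes, if serious |
| ADRs that caused discontinuation (tables, listing) | Yes | No |
| Serious ADRs that caused discontinuation (tables, listing) | Yes | No |
| Causality breakdown of discontinuation AEs | Uses the causality value itself | Possibly, as a missing line; the SAP does not require one |

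Nothing in SAP 6.4.1 or 6.6, or in Protocol 9.7.1 or 11.1.3, assigns a blank to any causality category or gives it a line of its own in the ADR rows.

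**Step 2: denominator.** The ITT set at week 8 is everyone dosed at least once (SAP 2.5.1), and up to 147 subjects are planned. The 5% drop-out allowance in the study-size section should not be taken off. Subjects who stop adalimumab are drop-outs by definition, and they are the subjects counted in these rows. If fewer than 147 are dosed, each subject weighs slightly more.

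**Step 3: size.** The documents give no AE count, no ADR rate and no expected share of blanks, so there is no planned figure to reproduce. What follows is illustration.

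- One subject: 1/147 = 0.68, about 0.7 percentage points.
- Assume 8 subjects with an ADR that caused discontinuation, one event each, and assume the blank events would otherwise have carried one of the four labels:
  - no blanks: 8/147 = 5.4%
  - 1 blank: 7/147 = 4.8%, a loss of 1/8 = 13% of ADR subjects
  - 3 blanks: 5/147 = 3.4%, a loss of 3/8 = 38%
- Alternatively, assume 20 AEs that caused discontinuation, one per subject, with 0%, 5%, 10% or 20% blank. Then 0, 1, 2 or 4 events are left out of the ADR row, which is 0, 0.7, 1.4 or 2.7 points (0/147, 1/147, 2/147, 4/147).

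A blank event that would have been judged unrelated causes no loss. A subject with a second discontinuation AE that has a qualifying label still counts once. Both facts reduce the effect.

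**The case against.** The strongest reply is that blanks may hardly occur. Protocol 9.8 provides for review of case report forms for completeness, queries answered by the sites, double-key entry and logic checks. In Protocol 10.0, the sentence waiving monitoring is followed by one providing an internal consistency check. The affected rows hold only events that ended treatment. Protocol 9.7.1 says those events are collected and tabulated, and Protocol 11.1.5 has serious AEs actively solicited and notified within 24 hours. The event that led to stopping also precedes or coincides with the drop-out, so the limit on later data does not by itself produce a blank. All this stands and bears on frequency. It does not supply a rule for a blank that survives the queries.

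Three stronger readings are tempting, and the documents do not support them.

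- *The SAP classes a blank as unrelated.* It does not; section 6.6 assigns it no value. The result matches that of an unrelated event only in the ADR and serious-ADR rows and listings.
- *The event disappears from safety reporting.* It does not. It stays in the AE and serious-AE totals and listings. A careful reader could also find it as a missing category in the causality breakdown, or as a gap between that breakdown and the AE total.
- *The two rules contradict each other.* They can both be applied as written. Their joint result is merely out of line with the inclusive definition.

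It can also be said that not assessable is a judgement, whereas a blank is the absence of one, and that a separate missing line would respect section 6.6 more literally. That is a fair alternative. It would show the blanks but leave the ADR rates at their lowest possible value.

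**Conclusion.** The point holds as a small gap with a known direction. As written, the ADR and serious-ADR rows for discontinuation events give a lower bound whenever causality remains blank, while the SAP's definition otherwise leans toward inclusion. Each affected subject is worth about 0.7 points on an ITT set of 147. The fall from 5.4% to between 4.8% and 3.4% rests on an assumed 8 ADR discontinuations, an assumed 1 to 3 blanks, one event per subject, and blanks that would otherwise have qualified as ADRs. None of these figures comes from the documents. The frequency of blanks is unknown and may be zero, in which case nothing changes. The effectiveness results, the AE and serious-AE rows and the rates per 100 patient-years are untouched.

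**What to change.** Amend the safety bullet in SAP 6.6 to say that an AE whose causality is still missing after query is counted as an ADR, and as a serious ADR if it is serious, in line with the not-assessable category. Show the number of events and subjects counted in this way under each ADR table. All other missing safety values stay unreplaced.

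The cost is one sentence and one table footnote, with no new data. The downside is that the ADR count may be slightly less favourable and may include events that would have been judged unrelated. The printed number lets a reader subtract them. Settling the rule before the counts are seen avoids a choice made afterwards.

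One related matter should be reconciled at the same time. Protocol 11.1.3 defines a two-level causality scale (reasonable possibility or not), and its levels do not map onto the four labels in footnote a. The SAP should say how one translates to the other, because the ADR definition cannot be applied directly to data recorded on the protocol's scale.
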